1.3 Safety

Risks

This study presents minimal potential risks to participants. There are no alternatives to these data collection procedures. Participants may choose to not participate in any part of this voluntary study. Potential risks include: Discomfort during completion of study questionnaires or

cognitive testing, and/or discomfort related to sleep studies or wearing PSG equipment. The study team will take all reasonable steps to minimize these risks.

Study Questionnaires: The questionnaire battery, which requires the participants to reflect upon and report on their physical and emotional symptoms may cause mild emotional distress. Baseline and follow up questionnaires are expected to take approximately 30 minutes on average; during this time, participants may experience physical pain, fatigue, or boredom. Participants will have the option to take breaks and may elect to complete the questionnaires on another day if they are too tired or distressed. In addition, the names and contact information of the study team will be noted on the consent form and participants can contact them if needed.

Cognitive Testing: Cognitive testing is expected to take the average participant approximately 90 minutes to complete. During that time, it is possible that the participant may experience discomfort in the form of fatigue, physical pain, or boredom. In addition, if the participant perceives that they are not performing well, they may feel frustrated or emotionally distressed. The examiner who administers the cognitive tests will monitor the participant for signs of discomfort and distress and, as needed, will offer breaks and/or encouragement in the form of normalizing any emotional distress. In the event that a participant becomes extremely physically or emotionally uncomfortable, he or she may elect to discontinue testing or continue the remainder of the testing on another day.

In-laboratory overnight Polysomnography (sleep study) and Positive Airway Pressure (PAP) titration: The baseline sleep study (PSG) should not be painful and generally has few complications. Sensors or electrodes are placed on the scalp, face, chest, limbs, and a finger. The equipment records brain activity, eye movements, chin muscle activity, heart rate and rhythm, blood pressure, and the amount of oxygen in your blood. Elastic belts are placed around the chest and belly to measure chest movements and the strength and duration of inhaled and exhaled breaths. Additional sensors will measure airflow at the nose and mouth. Wires attached to the sensors transmit the data to a computer in the next room. The wires are very thin and flexible. They are bundled together so they don't restrict movement, disrupt sleep, or cause other discomfort. The most common side effect is mild irritation where electrodes come in contact with the skin. It may also be stressful to sleep away from the comfort of the subject's normal sleep environment. Subjects may sleep poorly in the lab, and as a result feel sleepy on the day after the study. For this reason, subjects are encouraged to ask someone to drive them to the sleep laboratory and take them home on the next morning. Skin integrity is checked by the sleep technologists. If subjects have a skin reaction at the site of a sensor used to monitor sleep or heart rate, the technologist will move it to another site and use a different type of tape or glue. If subject's skin should become irritated at multiple sites or in any severe manner, the study will be stopped. Any skin irritation at sites where sensors were placed is expected to resolve after the study on its own, usually in hours or at most a day or two.

Unless already performed for clinical purposes at U-M Sleep lab within the past year, participants who are diagnosed with OSA on baseline PSG will then undergo PAP titrations* to determine the ideal PAP machine setting(s), and participants will be prescribed clinical CPAP or BiPAP machines by clinicians involved in the study or their clinical sleep provider.

PAP therapy is considered standard clinical care for OSA. It involves wearing an apparatus that includes a hose and a mask (that covers the nose, or nose and mouth), connected to a small machine that blows air into the airway during sleep. The degree of air pressure given depends on the subject's apnea severity, and the supplied air pressure can be continuous or change with the subject's breathing pattern. This in-laboratory PAP titration sleep test uses the same sensors and has the same complications as the baseline sleep study, but the subject will also wear a mask attached to a PAP machine during sleep for this test, so that the sleep technicians can determine which type of mask and airway pressure are most appropriate. Masks can be uncomfortable and create a feeling of claustrophobia. Air pressure may dry out nasal passages. Subjects will be encouraged to alert the staff in the sleep laboratory to any other concerns, discomfort, or complications that arise during the PSG or PAP titration. A doctor will always be on call for any unexpected health emergencies.

*In some cases, insurance carriers will not cover the cost of an in-laboratory PAP titration, and instead will recommend an "auto-adjusting" PAP machine (also known as AutoPAP, or APAP) so that patients diagnosed with OSA may begin PAP without requiring a PAP titration. AutoPAP differs from a CPAP in that it uses algorithms to sense subtle changes in the user's breathing and deliver only the amount of pressure necessary to keep the airway open. AutoPAP can be also set to a straight CPAP mode, if determined necessary by the sleep provider, therefore offering more flexibility than a CPAP or BiPAP machine. In cases where AutoPAP is recommended by the participant's insurance carrier and no medical or PSG contraindications to AutoPAP exist, participants will be allowed to waive their in-lab PAP titration and start AutoPAP therapy according to their PAP randomization assignment.

PAP Therapy: There may be skin irritation related to the **PAP** mask, and masks can be uncomfortable and create a feeling of claustrophobia. There are multiple choices and sizes for sleep masks, and the provider will work with the subjects to find the most comfortable mask. There may be difficulty tolerating the forced air, but the pressure settings can be adjusted by working with the sleep machine provider. Subjects might experience a dry stuffy nose which can be treated with a saline nasal spray or humidified air that can be run through the PAP machine. The providers of these machines are very familiar with resolutions to and they will try and assist subjects in order to resolve any issues.

Confidentiality: The records of this study will remain confidential and protected; however, there is a risk for a breach of confidentiality. This risk is minimal, because a number of precautions have been taken in order to protect confidentiality. All data collected will be kept secure and in a locked office. Records will be coded and identifying information (such as name and registration numbers) will be removed and stored on a key in a separate location so that confidential information cannot be traced back to the subject. Only authorized members of the research team will have access to study records.

Standard care PAP treatment arm (for Group 2): Given that most consequences of OSA take months to years to manifest (cardiovascular disease, metabolic syndrome), we do not anticipate any significant long-term side effects from deferring PAP for 3 months for Group 2. Identification of sleep disordered breathing will be facilitated by enrollment into this study. Nonetheless, to avoid hazardous short-term consequences of OSA caused by excessive

sleepiness (e.g., motor vehicle accidents), ESS scores ≥ 16 on baseline or follow-up visits will be cause for study exclusion/discontinuation. This cutoff was chosen based on data that demonstrate an ordinal increase in risk of sleepy driving accidents with increases in ESS score, particularly in subjects with ESS scores > 15 . We will also consider extreme OSA (RDI >60 respiratory events per hour, or unstable ECG rhythms on PSG) to be exclusionary, regardless of ESS score. For subjects who are not considered to be high risk per these criteria, we do not expect the risk of participating in this trial and having no CPAP for 3 months to exceed the risk encountered in routine clinical practice, as wait times for sleep clinic evaluations, subsequent sleep clinic referral, PSG, CPAP titration, and CPAP initiation at home currently often amount to 3 months or longer at U-M sleep clinics.

Alternative treatments and procedures: This study does not include an intervention. Therefore, there are no applicable alternative treatments or procedures.

As with any research study, there may be additional risks that are unforeseeable.

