4.2 Exclusion Criteria

- 1) Physical, psychiatric or cognitive impairment that prevents informed consent, PSG, PAP use, or reliable longitudinal follow-up
- 2) Cardiopulmonary conditions that may increase sleep apnea risk
- 3) Current treatment, such as PAP, for obstructive or central sleep apnea
- 4) History of surgical treatment for OSA
- 5) Nervous system diseases other than MS that may predispose subjects to OSA (such as Parkinson's disease, amyotrophic lateral sclerosis, or recent stroke)
- 6) History of concomitant central nervous system disease that could influence cognition, such as large vessel territory stroke, Alzheimer's disease, Parkinson's disease, or Lewy body dementia
- 7) Concomitant systemic autoimmune disease with secondary central nervous system involvement (including CNS lupus or neurosarcoidosis).
- 8) Pregnancy
- 9) Evidence of clinical MS relapse within the last 30 days prior to enrollment
- 10) Systemic high dose steroid use (1 gram IV methylprednisolone daily for 3-5 days or equivalent) for an MS relapse within the last 30 days prior to enrollment
- 11) Unwillingness to initiate PAP therapy if clinically indicated
- 12) Severe depression at screening per the Patient Health Questionnaire-8 (PHQ-8)
(The PHQ-8 is a brief, self-administered questionnaire that evaluates core symptoms associated with major depressive disorder. Scores range from 0 to 24 based on the frequency and severity of depressive symptoms over the previous two weeks.)
- 13) Anticipated initiation, dosage change, or discontinuation in medications that could, per the opinion of the investigators, influence cognitive test scores from baseline to follow-up, including MS disease modifying therapies, hypnotic agents, narcotic-based medications, benzodiazepines, antispasmodics, or 4-aminopyridine
- 14) ESS scores ≥ 16 on baseline visit
- 15) Subjects with extreme OSA accompanied by signs of cardiopulmonary compromise (RDI > 60 respiratory events per hour with severe nocturnal hypoxia or unstable ECG rhythms on PSG), will be excluded unless they are randomized to immediate PAP arm
- 16) Any other condition or treatment that in the opinion of the investigator could affect subject safety or study eligibility

Table 1: STOP-Bang questionnaire	
Snoring	Do you snore loudly (louder than talking or loud enough to be heard through closed doors)?
Tired	Do you often feel tired, fatigued, or sleepy during the daytime?

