6.4 Randomization

Randomization Process/Blinding: Subjects who meet criteria for OSA on baseline or clinical PSG (n~140, anticipated) will be randomized (2:1 randomization) to determine whether they will receive expedited PAP therapy (Group 1, n~93), or standard of care PAP therapy (Group 2, n~47). Computer-based randomization will be stratified by sleep apnea severity (RDI $<$ or ≥ 30) to minimize imbalances in apnea severity between groups. PSG technicians, PSG interpreters, and study staff who conduct and score neuropsychological tests will remain blinded to group allocation for the duration of the study. The subject, PI, co-investigators, coordinators, and statistician will not be blinded. **Subjects will be contacted with the randomization**

assignment that determines whether they will be scheduled for immediate PAP titration (Group 1) or delayed PAP titration after their month 3 cognitive testing.

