6.6 Month 1 and Month 2 Follow-up Visits/Assessments

Group 1: 1 and 2 months following PAP initiation – *Group 1 subjects will have the option of doing their MONTH 2 assessment by phone or in person*

Group 2: 1 and 2 months following randomization – *Group 2 subjects will have the option of doing either of these assessments by phone or in person*

All randomized subjects will undergo the following assessments:

- 1) Focused medical and surgical history as it relates to MS, sleep, and cardiopulmonary history
- 2) Medication review
- 3) PAP compliance review (datacard assessment) for Group 1
- 4) Fatigue, insomnia, and sleepiness assessments (see 7.2)
- 5) AE/SAE review

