6.7 Month 3 Visit with repeat Cognitive Testing

Group 1: 3 months after PAP initiation

Group 2: 3 months after randomization

All randomized subjects will undergo the following assessments:

- 1) Focused medical and surgical history as it relates to MS, sleep, and cardiopulmonary history
- 2) Medication review
- 3) PAP compliance review for Group 1
- 4) Fatigue, insomnia, and sleepiness assessments (see 7.2)

- 5) Pain, anxiety, and quality of life assessments (see 7.2)
- 6) AE/SAE review
- 7) Repeat neuropsychological testing (see 6.2)
- 8) PAP titration for group 2 (if applicable)*

* Group 2 subjects are encouraged to undergo PAP titration on the night of the Month 3 visit. If they agree to this approach, the PAP titration will be scheduled around the time of the Month 2 visit.

6.8 Post-Study Follow-up phone assessment for Group 2 (1 month after Month 3 visit)

Following the Month 3 visit (and once the PAP titration is complete) , for Group 2 subjects who still express a desire to proceed with PAP treatment, the study team will contact the subject and/or DME company (phone or email) to confirm that a PAP prescription has been faxed to the subject's designated DME company), and if applicable, that UM sleep clinic follow up has been made. Three phone contacts will be attempted. Any barriers to the PAP prescription process will be passed on to sleep clinic staff for appropriate action. If no clinic follow up has been scheduled per the subject's account (and the subject still desires a sleep clinic appointment), the study team will contact appropriate UM sleep clinic personnel to contact the subject.

SCHEDULE OF ACTIVITIES

Study Activity	Baseline Visit	Baseline PSG visit	Month 0	Month 1	Month 2	Month 3
Demographics	X					
Medical/Surgical History	X			X	X	X
Medication review	X			X	X	X
Height, weight, neck circumference	X					
EDSS self-report	X					
AE/SAE review	X			X	X	X
Baseline neuropsych testing (all subjects)	X					
Repeat neuropsychological testing (OSA subjects)						X
Baseline PSG (all subjects who do not have U-M PSG within the past year)		X				
Randomization (for subjects with OSA on baseline PSG)			X			
PAP titration/prescription for Group 1			X			
PAP compliance review for Group 1				X	X	X
Fatigue (FSS), insomnia (ISI), and sleepiness (ESS) surveys	X			X	X	X
PROMIS/NeuroQOL measures	X					X

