13. STUDY DISCONTINUATION CRITERIA

Stopping Rules for Safety Reasons

Subjects who demonstrate evidence of severe excessive daytime sleepiness (as evidenced by ESS scores ≥ 16 at baseline) will result in exclusion from study. Subjects with extreme OSA that is accompanied by signs of cardiopulmonary compromise or severe nocturnal hypoxia on baseline PSG will also result in study exclusion unless they are randomized to expedited PAP arm. In such cases, subjects will be referred for expedited sleep clinic follow-up.

Discontinuation of a Subject

In the event a patient drops out of the study or is discontinued due to protocol violations, all attempts will be made to exit the patient in accordance with the protocol requirements.

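### The follow-up ESS ≥ 16 rule in Section 1.3 is not carried into the stopping rules (Section 13) or the visit procedures (6.6, 6.7), so its use during Group 2's 3-month deferral is ambiguous

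*Combined protocol and SAP*

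**What the plan says.** Section 1.3, in the paragraph on Group 2, names sleepiness-related driving accidents as the short-term hazard of deferring PAP. It then sets the safeguard: "ESS scores ≥ 16 on baseline or follow-up visits will be cause for study exclusion/discontinuation". Its statement that the deferral carries no more risk than routine practice is limited to subjects who are not high risk by the criteria listed there, and this is one of them.

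Section 13, under its heading on stopping for safety, restricts the cut-off to entry: "as evidenced by ESS scores ≥ 16 at baseline) will result in exclusion from study". Its text on later discontinuation starts from a different cause: "In the event a patient drops out of the study or is discontinued due to protocol violations".

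ESS is measured throughout. The schedule of activities lists "Fatigue (FSS), insomnia (ISI), and sleepiness (ESS) surveys" at baseline and Months 1, 2 and 3. In Section 6.6, for Months 1 and 2, "Group 2 subjects will have the option of doing either of these assessments by phone or in person". Neither 6.6 nor 6.7 says what happens when a score reaches 16. Section 6.4 assigns "immediate PAP titration (Group 1) or delayed PAP titration after their month 3 cognitive testing" and gives no exception.

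**The concern.** The argument that the deferral is safe depends partly on a rule that appears only in the background section. Staff who work from Section 13 and the visit procedures would find no instruction for a Group 2 subject whose ESS is, say, 17 at Month 1.

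Two things are at stake. The first is safety: a subject past the plan's own driving-risk limit could remain untreated while the score sits in the record. The second is the analysis. If 1.3 is applied and discontinuation means leaving the study, a subject is removed before the Month 3 battery because of something measured after randomization. Group 2 is untreated and is the smaller arm. The plan does not say whether PAP is then released, whether Month 3 testing still takes place, or how the subject is analysed. It is also unclear whether the rule covers Group 1, since the wording is general but the paragraph concerns Group 2.

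**Working it through.** **1. The texts side by side.**
- Section 1.3: baseline or follow-up; consequence is exclusion or discontinuation.
- Section 13: baseline only; consequence is exclusion, with expedited sleep-clinic referral.
- Section 4.2, criterion 14: "ESS scores ≥ 16 on baseline visit". This is an entry list, so a baseline limit is what one expects there.
- Sections 6.6, 6.7 and the schedule: ESS collected at Months 1, 2 and 3; no action.

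The gap is between 1.3 on one side and 13, 6.6 and 6.7 on the other.

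**2. Time at risk if no action follows.** For a Group 2 subject who crosses at Month 1, 3 − 1 = 2 further months to Month 3 testing.

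**3. The plan's power figure.** Inputs from Section 9.1: SD 9, difference 5, two-sided 0.05, 2:1 allocation (93 and 47). Noncentrality = 5 / (9 × √(1/93 + 1/47)) = 5 / 1.611 = 3.10 on 138 df, which gives 86.9% (plan: 86.3%). The plan's 81.2% after dropout is reproduced with 80 and 40.

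**4. Discontinued, Month 3 score lost.** The documents give no crossing rate. Assume k = 2, 5 or 9 of 47.
- If these subjects' scores are typical, 93 against 45, 42 or 38 gives 85.9%, 84.3% or 81.7%.
- If they would have scored lower, the Group 2 mean shifts. Section 9.2 adjusts for baseline score. With a deficit d present equally at baseline and Month 3, equal SDs, and pre/post correlation r, the shift is (k/47) × d × (1 − r). Assume k = 5, d = 4.5 points (half an SD) and r = 0.5 to 0.8; none of these is in the documents. The shift is 0.106 × 4.5 × 0.5 = 0.24 down to 0.106 × 4.5 × 0.2 = 0.10 points. If SD 9 refers to raw scores, the residual SD is 9 × √(1 − r²) = 7.79 or 5.40. Power is then 90.3% or 99.8%, against 94.5% or 99.9% with no loss.
- If the deficit arises only after baseline, adjustment does not remove it: the shift is 0.106 × 4.5 = 0.48 points, and power is 87.2% or 99.4%.

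**5. Kept in the study with early PAP.** The sample stays 93 and 47. With full benefit by Month 3 the difference is 5 × (1 − k/47); with half benefit, 5 × (1 − k/94). Unadjusted power, SD 9:

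| k | Full benefit | Half benefit |
|---|---|---|
| 2 | 4.79 points, 83.9% | 4.89 points, 85.5% |
| 5 | 4.47 points, 78.7% | 4.73 points, 83.1% |
| 9 | 4.04 points, 70.3% | 4.52 points, 79.6% |

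With baseline adjustment at r = 0.5, k = 5 gives 88.9% (full) or 92.1% (half), close to the 90.3% in step 4. Power therefore does not clearly favour either handling.

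**The case against.** The strongest reply is that the rule already exists. Section 1.3 states it for follow-up visits, in the paragraph about Group 2, and the scores needed to apply it are collected. A reader might infer that Group 2 has no rule at all, or that Section 13 tells staff to keep a sleepy subject untreated. The documents support neither: Section 13 is silent on follow-up scores, and silence does not cancel an explicit statement elsewhere. Nor does 4.2 contradict 1.3. All of this stands.

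There is also clinical cover. Section 10.1 puts every subject with OSA under a certified sleep provider, and Section 13 shows expedited referral as the route after a baseline exclusion. This helps, but neither text sets a follow-up threshold or says that the assigned deferral may end.

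It does not settle the matter that 1.3 is explicit. Sections 1.3 and 13 also differ on extreme OSA: 1.3 excludes on RDI above 60 alone, whereas 4.2 and 13 require signs of compromise and exempt the immediate-PAP arm. Staff could reasonably take the narrower sections as governing.

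On the analysis, a reader might infer that selective loss would seriously bias the SDMT comparison. The documents do not support that. The crossing rate and the deficit are both unknown, baseline adjustment removes much of any deficit already present at baseline, and removals from Group 1 as well would offset part of the shift. Section 9.1 already allows 10 dropouts per group, and every typical-score figure in step 4 lies above its 81.2%. One qualification remains: if these losses come on top of ordinary dropout, 79 against 36 gives 78.2%, compared with 81.0% for 79 against 40.

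Finally, replacing discontinuation with early PAP goes beyond tidying the text. It is a design choice and needs its own justification.

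**Conclusion.** The point holds as an ambiguity with a safety consequence. A rule that supports the deferral is stated in 1.3, is absent from the stopping rules and visit procedures, and has no defined consequence. A Group 2 subject who crosses at Month 1 could go 2 more months untreated, or could be removed before the outcome is measured, depending on which section staff follow.

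The effect on the primary comparison cannot be sized from the documents. With 5 of 47 crossing, a 4.5-point deficit and a correlation of 0.5 to 0.8, all assumed, the shift is 0.10 to 0.24 points of a 5-point effect if the deficit is already present at baseline, and 0.48 if it is wholly new. Baseline exclusion at the same cut-off means that only later crossers count, and there may be few of them. The change is worth making because it is cheap and because the safety case refers to this rule, not because the trial's power is threatened.

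**What to change.** In Section 13, cross-referenced in 6.6: ESS of 16 or more at Month 1 or 2 is scored at the time and reviewed promptly by a study clinician. In Group 2 the deferral ends and the subject is referred for expedited sleep-clinic follow-up to start PAP. In Group 1, PAP use and settings are reviewed. In both groups the subject has the Month 3 battery on schedule and is analysed as randomized, with the PAP start date recorded. Change the discontinuation wording in 1.3 to match. Exclusion 14 in 4.2 needs no change.

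The cost is a few sentences and prompt scoring, including at Group 2 phone contacts. No visit or test is added. The investigator and coordinators are already unblinded (5.2), so they can act without unblinding the raters.

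The statistical price is some dilution. For an assumed 5 of 47, the difference is 4.73 to 4.47 points instead of 5, with unadjusted power of 83.1% to 78.7%; at 9 of 47 with full benefit it falls to 4.04 points and 70.3%. In return, no subject leaves the comparison because of a post-randomization sleepiness score, and treatment is offered when the plan's own limit is reached.
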